4.8. Evaluation of clinical data relevant to the current clinical study

Prior to the CE marking of the product, a review of clinical data regarding safety and performance for TripleA and similar products is compiled in the Clinical Evaluation Report. In summary, there is limited data for equivalent products, as TripleA is a system with several components. There is dock data that supports each component itself is secure and has effects and features that can contribute to the composite system.

5. Risks and benefits of the test product and the clinical study

5.1. Expected clinical benefits

TripleA is expected to support the patient in his decision to reduce or completely abstain from alcohol consumption, by reducing the space where one can otherwise drink without anyone else finding out. Via TripleA, the therapist and patient also receive more reliable data on the patient's alcohol intake patterns and can, based on this, find strategies for managing risk situations. TripleA also means that any relapses can be noticed more quickly and further treatment can be initiated if necessary.

5.2. Expected side effects from the test product

The use of TripleA entails a significant restriction on the patient's privacy as information about alcohol intake is communicated to the care provider. However, this is one of the main points of the method and a prerequisite for the use of TripleA both within the framework of the current study and addiction care in general is that it is voluntary for the patient to use TripleA as enhanced support for other interventions.

Probably even a sober patient experiences a strong stress if you do not have the opportunity to perform a prescribed sobriety test within a given time, or discover that you have missed a test. How this is experienced will be mapped in focus group interviews. The patient is also given the opportunity to prove his sobriety by providing an extra blood sample if desired.

5.3. Remaining risks associated with the test product

For the risk management process, Kontigo Care has complied with the harmonized standard ISO 14971: 2012 Medical devices - Application of a risk management system for medical devices.

Appropriate measures have been taken for all foreseeable safety risks that could have been linked to the use of TripleA as intended, or that could arise in the event of a malfunction of any of the components in the system.

5.4. Risks associated with participation in the study

A safety aspect that should be taken into account for the relevant patient group is that an abrupt release of alcohol in people who have had a long-term and high consumption of alcohol is associated with a risk of severe withdrawal symptoms, which can be life-threatening. However, this is not linked to the use of TripleA per se, but a consequence of the release of alcohol.

5.5. Interactions

TripleA does not affect concomitant pharmacological treatment.

5.6. Risk reduction measures

Usual clinical procedures must be applied to manage the risks of discontinuation of alcohol and can e.g. be about gradual reduction of alcohol intake or hospitalization for detoxification.

5.7. Risk-benefit motivation

The benefit of TripleA is judged to outweigh the risks of the current patient population, especially given that the method in the current study does not replace any other treatment but is used as a supplement to, and reinforcement of, patients' regular care.

The risks mentioned in sections 6.3 and 6.4 above must also be set in relation to the consequences of continued alcohol consumption, both with regard to the patient's own health and for the co-dependents, consequences that may be considered significantly more serious.

6. The study's objectives and hypotheses

6.1. Objectives

6.1.1. Primary objective

The primary objective of the study is to investigate differences in alcohol consumption patterns between alcohol dependents who receive only conventional treatment and alcohol dependents who receive conventional treatment enhanced with TripleA.

6.1.2. Secondary objectives

- Examine whether more patients can achieve and maintain sobriety if conventional treatment is enhanced with TripleA
- Investigate whether TripleA can contribute to fewer patients relapsing and whether relapse can be delayed
- Investigate whether TripleA can help fewer patients discontinue treatment
- Collect data on health outcomes as a basis for health economic analyzes
- To use interviews to evaluate how users experience the product TripleA in different respects

6.2. Hypotheses

By strengthening TripleA with the conventional hospital care of alcohol addicts (medicines and therapy calls), a larger proportion of patients is obtained who significantly reduce their alcohol consumption or become completely sober, thereby reducing their risk of somatic and / or mental injuries.

6.3. Claims and performance to be verified

The desired effect of treatment for alcohol dependence is to improve physical and psychosocial parameters. As a surrogate variable, however, it is accepted that you measure changes in the drinking pattern, which can be either absolute sobriety, or a reduction in the number of heavy drinking days. Regardless of how one chooses to evaluate treatments for alcohol dependence, a basic attitude is that if the treatment does not change the drinking pattern in a positive direction, it has not been successful. In this verification study, the hypothesis is that the use of TripleA enhances conventional treatment so that the drinking pattern with TripleA means a clinically relevant reduction in alcohol intake, compared with the drinking pattern without TripleA. Clinically relevant is that heavy drinking days do not occur.

6.4. Risks and adverse effects

Experiences with regard to invasion of privacy, etc. will be mapped via questionnaires to the participating patients / focus group interviews.

Risks and expected undesirable effects of the test product are assessed in advance as small, but safety reporting during the course of the study is essential in order to be able to capture any unexpected effects and risks with TripleA. See also section 18 (Safety reporting).

7. Study design

7.1. Generally

7.1.1. Type of clinical study

The study is a 12-month open and randomized comparison between the control group receiving conventional therapy only and the intervention group receiving conventional therapy enhanced with TripleA.

The study is open because it is the overall concept TripleA that is to be evaluated, which means that both the patient and the therapist must use the tool. A single-blind design could have been used if the goal had been to study the system's components, e.g. only changed patient behavior due to increased support or how therapists' efforts change with or without the information that TripleA can provide. If you want to study the combination effect, the study cannot be blinded. Many treatments work to achieve sobriety or controlled drinking in the short term, but it is more difficult to maintain the effect over time, as the problems behind drinking do not necessarily disappear because you stop drinking or reduce your drinking. The EMA and the FDA, respectively, recommend 12 or 6-month studies, as the drinking pattern at these times has been shown to be predictive of long-term outcomes.

In the current studies, patients will be followed for 12 months to cover all the holidays of the year and other regularly recurring challenges for those who try to refrain from drinking alcohol. An interim analysis is performed after 6 months to obtain data that can support the system patent for TripleA.

7.1.2. Baseline

The process leading up to a treatment intervention can look very different for different patients. Some will therefore have been sober or significantly reduced alcohol consumption for a long time before it becomes relevant with visit 1. To then always use the 4 weeks preceding visit 1 as a baseline for Time Line Follow Back will be very wrong. It is therefore up to the care provider to, in consultation with the patient, define which four-week period is to be counted as the baseline in each individual case. It should be a continuous period of four weeks, and the most recent four-week period that has a representative alcohol intake pattern for the period before the decision to seek help / initiate treatment was made.

7.1.3. Measures taken to minimize or avoid bias/impact

7.1.3.1. Randomization

Randomization of study participants is important to avoid the caregiver consciously or unconsciously distributing TripleA treatment to a certain category of patients. The patient population is heterogeneous, but demographic and social differences between the study arms should be due to chance and not other factors. The randomization takes place according to the principle of permuted blocks in order to distribute the patients as far as possible so that the individual therapists do not treat only one study arm. Each caregiver will have access to their own randomization list. See also section 8.8.2.

7.1.3.2. Sampling as a complement to TLFB

The TimeLine Follow Back method relies on patients remembering and wanting to talk about their alcohol consumption. To improve reliability, TLFB will be combined with sampling of biomarkers for blood alcohol.

7.2. Efficacy endpoints

7.2.1. Primary efficacy endpoint

Proportion of patients who do not have heavy drinking days

Clinically relevant for treatment focused on risk reduction is that patients do not have heavy drinking days. The measurement tool will be TLFB (see Appendix C) where the number of days with large consumption over a four-week period is calculated.

Heavy drinking days are the same as days with heavy consumption, which means consumption of 4 or more standard glasses of alcohol per day for women and 5 or more standard glasses of alcohol per day for men.

How to determine the TLFB at baseline is stated in section 8.1.2. Follow-up TLFB is then made at each visit. The primary measure of effectiveness is the difference between the treatment arms in the proportion of patients who do not have heavy drinking days during the 4-week period preceding the 12-month visit.

7.2.2. Secondary efficacy endpoints

Difference between the treatment arms in the proportion of completely sober patients during a 4-week period at 6 and 12 months, respectively.

The proportion of completely sober patients is measured with TLFB. To be considered sober, the patient must have entered 0 standard glasses consumed during the 4-week period preceding the 6- and 12-month visits, respectively.

The difference in the total amount of alcohol consumed per 4-week period after 6 and 12 months, respectively, compared with baseline

The total amount of alcohol consumed per 4-week period is measured in standard glasses using TLFB, and is the sum of the number of glasses for the entire period. How to determine the TLFB at baseline is stated in section 8.1.2. Follow-up TLFB is then made at each visit. The difference in the number of heavy drinking days per 4-week period at 6 and 12 months, respectively, compared with baseline

The number of heavy drinking days is measured with TLFB. Heavy drinking days are the same as days with heavy consumption, which means consumption of 4 or more standard glasses of alcohol per day for women and 5 or more standard glasses of alcohol per day for men. How to determine the TLFB at baseline is stated in section 8.1.2. Follow-up TLFB is then made at each visit.

The difference in the number of drink-free days per 4-week period at 6 and 12 months, respectively, compared with baseline.

The measuring tool becomes TLFB where the number of days of consumption specified as zero standard glass during a four-week period can be calculated. How to determine the TLFB at baseline is stated in section 8.1.2. Follow-up TLFB is then made at each visit..

The measuring tool becomes TLFB where the number of days of consumption specified as zero standard glass during a four-week period can be calculated. How to determine the TLFB at baseline is stated in section 8.1.2. Follow-up TLFB is then made at each visit.

The measuring tool becomes TLFB, where the sum of the number of standard glasses for the entire 4-week period is divided by the number of days when alcohol is consumed. How TLFB is to be determined at baseline is stated in section 8.1.2. Follow-up TLFB is then made at each visit.

Time to relapse

Depending on the goal of treatment, a relapse can be either a day of heavy consumption or drinking at least one standard glass of alcohol. Both recurrence measures will be evaluated.

- The number of days before the first alcohol intake (at least one standard glass) according to the patient's own information.
- The number of days before the first heavy drinking day according to the patient's own information.

Clinical Global Impression improvements after 6 and 12 months, respectively

The patients who after 12 months are "significantly improved" or "greatly improved", ie they receive a value of 1 or 2 on the CGI-I scale (see section 8.3.6) are considered to have responded to the treatment (responders). Patients with a value of 3 or higher are classified as non-responders. The proportion of responders will be compared between the treatment arms.

Change in quality of life measured with EQ-5D

EQ-5D is an accepted and widely used measure of quality of life, and the form is recommended by TLV (Dental and Pharmaceutical Benefits Agency). A general quality of life measure such as EQ-5D provides an overall picture of the study participants' perceived health, and is a good basis for health economic analyzes.

AUDIT improvement

The National Board of Health and Welfare prioritises AUDIT as a tool for identifying alcohol problems. The treatment arms will be compared with respect to:

- Proportion of patients who after 12 months have lowered their AUDIT score
- Proportion of patients who after 12 months have lowered their AUDIT score to at least one zone
- Proportion of patients who after 12 months have a risk level <II
(i.e. less than 6 AUDIT points for women, 8 AUDIT points for men).

SADD improvement

Change in alcohol dependence measured as the difference in SADD scores at 12 and 6 months, respectively, compared with baseline).

Compliance with agreed treatment

The patient remains in treatment

At each study-related visit, it is documented whether the patient remains in treatment or has interrupted his or her treatment. The proportion of patients who remain in treatment will be compared between the patient groups over time.

Compliance with TripleA

For the TripleA arm, the proportion of measurements performed compared to announced measurements will be reported. The information is retrieved from the TripleA database where all notifications and measurements are logged. Corresponding information is not available for the control arm for obvious reasons.

If the patient has a valid explanation for the lack of an individual blow, the caregiver can state this in the system, and indicate whether or not there should have been alcohol in the exhaled air at the time in question.

Compliance with the agreed plan for visits to the care provider and / or visits to AA meetings

In cases where the caregiver and patient have agreed that the patient should participate in certain activities, such as e.g. relapse prevention course or MI call, compliance with this plan will be evaluated. The ratio between the number of occasions the patient participated relative to the planned number is calculated and expressed as a percentage. The calculation is made per type of activity, eg:

- The number of treatment meetings that the patient has participated in the last 4 weeks divided by the number of planned treatment meetings for the corresponding period.
- The number of AA meetings visited in the last 4 weeks divided by the agreed number of AA meetings the patient would have attended for the corresponding period.

For the TripleA arm, this information can be retrieved from the TripleA database if that function has been used. However, the comparison between the treatment arms is based on the information noted in the CRF during the visits when the patient is asked about his or her participation. For the TripleA arm, an analysis is then made of how large the correspondence is between the registrations in TripleA and the data in CRF.

Compliance with drug treatment

Adherence to drug treatment will not be evaluated in the context of the study.

Change in the presence of the alcohol metabolites PEth and CDT in the blood at 6 and 12 months, respectively, compared with baseline.

Phosphatidylethanol (PEth) is analyzed at Karolinska Laboratory. The concentration of PEth-16:0/18:1 is given in the unit $\mu\text{mol} / \text{L}$. The PEth level in the blood reflects the alcohol consumption of recent weeks. PEth-16:0/18:1 values lower than $0.05 \mu\text{mol} / \text{L}$ indicate no or low sporadic alcohol consumption. Values between $0.05-0.30 \mu\text{mol} / \text{L}$ speak for regular moderate consumption, but even occasional very large intakes of alcohol can probably give measured values in this range.

Low carbohydrate transferrin (CDT) shows alcohol-induced change in the glycosylation pattern of transferrin, which is measured in serum samples. CDT is used as a marker to demonstrate regular alcohol consumption and «risk use / abuse», where the measured value reflects the intake during the last weeks - the month. Single major alcohol intakes do not affect CDT levels.

Analyzed at the Academic Laboratory and reported in%. Reference interval $<2.0\%$.

7.3. Methods and times for measuring, registering and analyzing variables

7.3.1. Short Alcohol Dependence Data (SADD)

SADD consists of 15 questions that measure the degree of alcohol dependence using a points scale. The form can be answered by the therapist interviewing the patient or filling in by the patient himself. Estimated time consumption max 5 minutes. See Appendix B

Time: Made at visit 1 to collect baseline data, and at 6 and 12 months.

7.3.2. Alcohol calendar– Time-Line Follow-Back

Time-Line Follow-Back (TLFB) is a method that can be used to obtain information about patients' alcohol consumption. (Sobell, Maisto et al 1979). In short, it means that as far back as 3 months ago, you retrospectively reconstruct how many standard glasses you have consumed per day. It is accepted that the reporting is not an exact representation of the alcohol intake, but also that it

provides a decent benchmark, which is also sensitive to changes in the drinking pattern. An alcohol calendar (see Appendix C) is used for this purpose. For study purposes, alcohol consumption reported via TLFB is used for the 4 weeks preceding each visit. How to determine the TLFB at baseline is stated in section 8.1.2.

When filling in TLFB, the patient and therapist must consult and results of blood tests and for the intervention arm, TripleA measurements must also be taken into account to identify if and when alcohol intake has occurred.

Information about missed measurements or measurements that show alcohol in the exhaled air (both for TripleA and for regular measurements at the care provider) should be used in the TLFB call and should in the alcohol calendar correspond to a number greater than 0 standard glasses on the current day. There may be discrepancies between what the patient is willing to state in the TLFB and the information that the caregiver has available in the TripleA caregiver portal or from other sources. The caregiver should talk to the patient about this, and give the patient the opportunity to update the information in the TLFB if necessary, but should not force the patient to enter a number greater than 0 or change information provided by the patient without the patient's consent.

In CRF, it is possible for the care provider to state whether there are signs of alcohol intake that do not correspond to reported intake in TLFB.

Time: At each visit.

AUDIT (The Alcohol Use Disorders Identification Test)

AUDIT (See Appendix D) is a well-validated instrument that is useful for identifying both alcohol problems and high alcohol consumption. However, AUDIT is not a diagnostic tool. You get a picture of consumption and the degree of difficulty of the problem. AUDIT consists of ten short questions and check boxes for the answers. It takes 2-3 minutes to answer the form that deals with last year's alcohol consumption. The first three questions are about how often and how much you drink, the rest about the consequences of drinking.

Time: Made at visit 1 (refers to the year before baseline), 5 and 6.

Risknivå	AUDIT-poäng	Tolkning
Zon I	Man 0-7 Woman 0-5	Low risk alcohol habits
Zon II	Man 8-15 Woman 6-13	Risky alcohol habits with not necessarily an addiction
Zon III	Man 16-19 Woman 14-17	Problematic alcohol habits likely there is an alcohol-related diagnosis
Zon IV	Man 20+ Woman 18+	Very problematic alcohol habits probably exist one alcohol-related diagnosis

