7.8.4. Visit 2 (Follow-up after 1 month)

- TLFB - See section 8.3.2 and Appendix C.
- Blood test - See section 8.3.8.
- Note changes in medication and other conventional treatment. Update relevant assessment phase information (WP2 only) - See sections 8.3.9 and 8.3.10
- Compliance - See section 8.3.12
- Safety reporting - See section 18

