7.8.5. Visit 3 (Follow-up after 2 months)

- TLFB - See section 8.3.2 and Appendix C.
- Blood test - See section 8.3.8.
- Note changes in medication and other conventional treatment. Update assessment phase information if relevant - See sections 8.3.9 and 8.3.10
- Compliance - See section 8.3.12
- Safety reporting - See section 18

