7.8.6. Visit 4 (Follow-up after 3 months)

- TLFB - See section 8.3.2 and Appendix C.
- Blood test - See section 8.3.8.
- Note changes in medication and other conventional treatment. Update the assessment phase information if relevant - See sections 8.3.9 and 8.3.10
- Compliance - See section 8.3.12
- Safety reporting - See section 18

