9.1.2.2. Secondary efficacy endpoints

- i) Change in total amount of alcohol consumed per 4-week period after 6 months from "baseline." An ANOVA model for repeated measurements will be used to compare the groups.
- ii) Change in total amount of alcohol consumed per 4-week period after 12 months from "baseline." An ANOVA model for repeated measurements will be used to compare the groups.
- iii) Proportion of completely sober patients at 12 months A logistic regression model will be used to compare the groups.
- iv) Proportion of completely sober patients at 6 months. A logistic regression model will be used to compare the groups.
- v) Change from baseline in the number of heavy drink days per 4-week period at 6 and 12 months, respectively. An ANOVA model for repeated measurements will be used to compare the groups.
- vi) Change from "baseline" in the number of non-drinking days per 4-week period at 6 and 12 months, respectively. An ANOVA model for repeated measurements will be used to compare the groups. Förändring från "baseline" i antalet standardglas per dryckesdag per 4-veckorsperiod vid 6 och 12 månader, respektive. vii) Time to relapse (ie first alcohol intake). For

patients with the goal of becoming alcohol-free, relapse is defined as the first day after "baseline" where alcohol consumption was found, while relapse for patients with the goal of reducing alcohol consumption is defined as the first day after "baseline" where heavy alcohol consumption is found. Heavy consumption is defined for women as a day with 4 or more glasses, while for men it is defined as a day with 5 or more glasses. The data sources TripleA, TLFB or blood samples are used to detect recurrence. To compare the survival curves, ie. the variable time to recurrence, between the treatment groups a log-rank test will be used.

- vii) CGI improvement. The proportion of respondents at follow-up visits is compared between the groups with a logistic regression model.
- viii) EQ-5D. The groups are compared regarding change from "baseline" with ANOVA model. No significant difference is expected, as quality of life forms are generally not particularly sensitive to change after treatment.
- ix) Participation in treatment. To compare the survival curves, ie. the variable time until the treatment is stopped, between the treatment groups a log-rank test will be used.

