3. Skriv in dessa händelser i alkoholkalendern fyra veckor bakåt och fram till dagens datum. Med hjälp av detta är det sedan lättare att komma ihåg när, hur och hur mycket alkohol du druckit.
4. Ta en vecka i taget och försök komma ihåg vilka dagar du druckit alkohol och mängden räknat i glas (se fig. nedan). Skriv i för varje dag hur många glas du druckit. Det är viktigt att alla rutor fylls i (de dagar du inte druckit skriver du 0).
5. Börja med den senaste hela kalenderveckan, dvs. måndag till söndag. Gå därefter bakåt en vecka i taget. Vecka 1 är den senaste veckan; vecka 2 är veckan dessförinnan; vecka 3 är veckan dessförinnan den osv.

MED ETT GLAS MENAS:

VECKA	MÅNDAG	TISDAG	ONSDAG	TORSDAG	FREDAG	LÖRDAG	SÖNDAG	SUMMA ANTAL GLAS PER VECKA
1								
2								
3								
4								

GLAS/VECKA

Lägg samman antalet glas för hela perioden (4 veckor):

Dela totala antalet glas med 4:

GLAS/DRYCKESDAG

Räkna antalet dagar som du druckit någon alkohol:

Dela antalet glas för hela perioden (se ovan) med antalet dagar som du druckit någon alkohol:

DAGAR MED STORKONSUMTION

(Kvinna) Dagar då du druckit 4 eller fler glas:

(Man) Dagar då du druckit 5 eller fler glas:

Bilaga D

AUDIT

Här är ett antal frågor om Dina alkoholvanor

Vi är tacksamma om Du besvarar dem så noggrant och ärligt som möjligt genom att markera det alternativ som gäller för Dig.

Med ett "glas" menas:									
	50 cl folköl		33 cl starköl		1 glas rött el vitt vin		1 litet glas starkvin		4 cl sprit, t. ex. whisky
Hur gammal är du?  år		Man 		Kvinna 					
1. Hur ofta dricker Du alkohol?	Aldrig 	1 gång i månaden eller mer sällan 	2-4 gånger i månaden 	2-3 gånger i veckan 	4 gånger/vecka eller mer 				
2. Hur många "glas" (se exempel) Dricker Du en typisk dag då Du dricker alkohol?	1 - 2 	3 - 4 	5 - 6 	7 - 9 	10 eller fler 				
3. Hur ofta dricker Du sex sådana "glas" eller mer vid samma tillfälle?	Aldrig 	Mer sällan än en gång i månaden 	Varje månad 	Varje vecka 	Dagligen eller nästan varje dag 				

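### Time to relapse is compared by a plain log-rank test, but self-report dates drinking on at most 140 of 365 days and no rule covers relapses in the gaps

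*Combined protocol and SAP*

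**What the plan says.** - **Endpoint.** Section 7.2.2 defines two relapse times by self-report, one to the first drink and one to the first heavy day: "The number of days before the first heavy drinking day according to the patient's own information". Section 9.1.2.2 takes the first qualifying day after baseline, with the definition depending on the treatment goal. It draws on TripleA, TLFB or blood samples.
- **Test.** Section 9.1.2.2: "the variable time to recurrence, between the treatment groups a log-rank test will be used". No censoring rule or dating rule is given.
- **Self-report.** Section 7.3.2 says of the method in general that "as far back as 3 months ago, you retrospectively reconstruct how many standard glasses you have consumed per day", then sets the study rule: "For study purposes, alcohol consumption reported via TLFB is used for the 4 weeks preceding each visit". The calendar form (Appendix C, in Swedish) has four weekly rows and tells the patient to work four weeks back from the current date: "Skriv in dessa händelser i alkoholkalendern fyra veckor bakåt och fram till dagens datum".
- **Visits.** Follow-up visits are at months 1, 2, 3, 6 and 12 (sections 7.3.14 and 7.8.4 to 7.8.8). None of the listed visit steps asks for the date of a first relapse outside the four-week window.

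**The concern.** A log-rank test on the day of first relapse needs to know, for each patient and each day, whether relapse has already happened. On self-report that is known almost continuously to month 3 and then for only two four-week blocks. A first relapse in a gap is either dated to the next window in which the patient drinks, or never recorded if the patient is dry in the later windows. A patient who relapses briefly in months 7 to 10 and is dry before month 12 would count as relapse-free on TLFB.

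Section 6.1.2 makes delay of relapse a secondary objective. Delay within a gap cannot be seen: recorded events pile up in the four weeks before months 6 and 12. The curves, the medians and the share relapsed are all affected.

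**Working it through.** **The plan's own figure.** The plan gives no event count or power for time to relapse. Its only sizing is for the primary endpoint (section 9.2), and this reproduces: [1.96 × √(2 × 0.45 × 0.55) + 0.842 × √(0.3 × 0.7 + 0.6 × 0.4)]² / 0.3² = 42 per arm; 42 / 0.8 = 52.5, so 53 per arm and 106 in total. Nothing in it changes.

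**Days covered.** Take visit 1 as day 0 and the visits as days 30, 61, 91, 183 and 365, each with a 28-day window ending on the visit day. The windows do not overlap, so coverage is 5 × 28 = 140 of 365 days (38%).

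| Period | Days | Covered | Share |
|---|---|---|---|
| To month 3 (1-91) | 91 | 84 | 92% |
| Months 3-6 (92-183) | 92 | 28 | 30% |
| Months 6-12 (184-365) | 182 | 28 | 15% |
| After month 3 (92-365) | 274 | 56 | 20% |

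The long gaps are days 92-155 and 184-337. Missed visits reduce coverage further.

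**Share of first relapses in the gaps.** The plan gives no relapse rate, so this is assumed. For a survival function S, the share of first relapses after month 3 that fall on uncovered days is

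{[S(91) − S(155)] + [S(183) − S(337)]} / [S(91) − S(365)].

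With a constant hazard and 70% relapse by day 365, h = −ln(0.3)/365 = 0.00330 per day. This gives S(91) = 0.741, S(155) = 0.600, S(183) = 0.547, S(337) = 0.329 and S(365) = 0.300, so (0.141 + 0.218) / 0.441 = 81%. Every such relapse is misdated or missed on TLFB alone.

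Across constant and falling hazards (Weibull shape down to 0.5) and 12-month risks of 50-90%, the share is about 80-84% after month 3. Over the whole year it is about 39-58%, lower when relapse comes early.

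**Misdated or missed.** This depends on how often a relapsed patient has further relapse days (assumed). Simulation for first relapses after month 3, constant hazard, 70% risk:

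| Further relapse day every | Correct | Misdated | Missed | Median delay if misdated |
|---|---|---|---|---|
| 90 days | 19% | 28% | 53% | 86 days |
| 30 days | 19% | 58% | 24% | 75 days |
| 7 days | 18% | 81% | 1% | 59 days |

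**Median time to relapse**, with 1-8 heavy days per 28 days after relapse (assumed):

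| Scenario | True | Recorded |
|---|---|---|
| Constant hazard, 70% | 210-214 days | 337-348 days |
| Constant hazard, 85% | about 130-135 | about 160-175 |
| Shape 0.5, 90% | 34 | 36-45 |

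The shift therefore runs from 36 − 34 = 2 days to 348 − 210 = 138 days, a little over four months.

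**Comparison between arms.** With no true effect, 42 per arm and 1,000 runs, the log-rank test rejects in 5-7% of runs when both arms have the same gaps. If TripleA days are counted in the intervention arm only, with detection assumed perfect, it rejects in about 8%, 25% and 59% when further relapse days come every 7, 30 and 90 days, with TripleA appearing worse. These last figures are illustrative.

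**The case against.** **Other sources.** A reader might infer that nothing is recorded in either arm between the windows. The documents do not support that. Section 9.1.2.2 names TripleA as a source, and section 7.3.12 has daily tests in that arm. The statement is true of self-report only. Blood samples do not close the gap: section 7.3.7 says PEth reflects recent weeks and CDT does not respond to single large intakes, so neither dates a relapse.

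**A date may be collected elsewhere.** Section 7.2.2 does not name TLFB for the relapse items, and the CRF is not among the documents, so a date field cannot be excluded. What stands is that no form, visit step or rule shown collects one. The question in section 9.2 that reaches back to the last contact is for patients leaving the study and asks for a maximum, not a date. Multiple imputation there covers discontinuation and missed visits; it does not cover days the calendar never asks about.

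**Treatment of unobserved days.** That they count as relapse-free time at risk is an inference from an unmodified log-rank test, not a statement in the plan.

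**Early relapse.** Participants must have drunk in the baseline period, so early relapse is plausible, and the first 91 days are well covered. In the shape-0.5, 90% case about 76% of first relapses occur by day 91. About 40% over the year are misdated or missed, but only 19-32% are more than 14 days late or missed; much of the rest is the two- or three-day slack between 28-day windows and calendar months. This limits the whole-year figures but not those after month 3.

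**Conclusion.** The point holds for a secondary endpoint. The day count needs only visits on schedule: at most 140 of 365 days, and 56 of 274 after month 3. That about 80-84% of first relapses after month 3 would be misdated or missed on TLFB alone rests on assumed hazards but was stable across those tried. The effect on the year as a whole and on the median depends on how early relapse occurs.

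Three stronger readings should be resisted:

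- A recorded median of 337-348 days against 210-214 is one scenario, in which the true median falls in the longest gap.
- About 14% of relapsers never being recorded (70% risk, constant hazard) needs a rate as low as one heavy day per 28 days; at four per 28 days it is below 1%.
- Equal gaps do not by themselves invalidate the test. They damage the curves, the medians and the ability to see delay.

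The comparison itself is at risk if TripleA days are counted as section 9.1.2.2 allows, because the gaps then fall mainly on the control arm. Sections 7.2.2 and 9.1.2.2 must be reconciled. The primary endpoint uses only the four weeks before month 12 and is unaffected.

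**What to change.** 1. State one set of data sources for time to relapse, the same in sections 7.2.2 and 9.1.2.2.
2. At every visit from visit 2, ask both arms whether they have drunk, and whether they have had 4 or more (women) or 5 or more (men) glasses in a day, since the last visit, and the date of the first such day if known.
3. Replace the plain log-rank test by an interval-censored log-rank test. The interval runs from the last day known to be relapse-free to the first day on which relapse is known.
4. Use an exact date only when it lies in a TLFB window with no unobserved gap before it, or is confidently recalled. Add a sensitivity analysis that treats all recalled dates outside the windows as interval-censored.

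The cost is a short CRF item within the existing TLFB conversation, plus SAP wording; no visits or patients are added. The limit is recall. Section 7.3.2 describes TLFB as reaching back about three months, and the last interval is six. Answers may also differ by arm, because section 7.8.11 expects TripleA monitoring to change reporting. Interval censoring allows for an imprecise date but does not correct a false report of no drinking.
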